2.1. Consent and Randomization

Informed consent and randomization will occur at the point of care using internet-based methods and traditional consent materials supported by treating clinicians and site coordinators. The consent process will adhere to requirements of the governing IRB and state laws. The CC will design and deploy a suite of best practice communication tools for use at enrollment. These tools will include a range of materials, e.g., consent forms, guides for physician-patient conversations and staff instructions, and supporting explanatory materials for patients and their caregivers. Materials will include information about potential adverse effects and out-of-pocket costs. The study tools are designed to work together to support and prepare the physician and staff to efficiently implement the study into routine healthcare environments. Best practice communication tools will help clinical staff organize the conversation with patients and colleagues and set realistic expectations with patients regarding their role and the potential study burden with supporting tools for patients and caregivers. The tools will contain clear instruction for staff and provide background and guidance to help them understand their role and how to facilitate using the study portal for collecting patient data. For patients, tools will include print and online information on COPD management, the RELIANCE trial, and the resources available from the PPRN and COPD Foundation. All patient-facing materials and tools will be submitted for IRB review prior to use.

Consent will be obtained prior to enrollment in the trial. Each patient will then be registered in the RELIANCE Portal by the Site Coordinator. Baseline data will be collected via the Participant Portal or Investigator Portal after the patient signs the consent statement for the trial. Baseline data will include demographic and personal information including social security number and health insurance provider. Eligibility will be confirmed via the Investigator Portal prior to randomization. After eligibility is confirmed, the patient will be randomly assigned to receive a prescription for azithromycin or roflumilast via the Investigator Portal. Once the assignment is released, the clinician, Site Coordinator, and the patient will be unmasked, i.e. will be aware of the treatment assignment. After the treatment assignment has been made, the patient is enrolled in the trial and will be followed regardless of treatment adherence. The clinician will prescribe either azithromycin (250 mg/day daily, 500 mg/day three times per week, or an alternate regimen) or roflumilast (250 mcg/day x 4 weeks, then 500 mcg/day or an alternate regimen) according to the random treatment assignment. Clinicians may tailor the treatment regimen to fit the patient's personal characteristics. Tailoring may include starting with a lower dose or a different dosing schedule. Once the prescription has been dispensed, the Site Coordinator will enter the prescription as written by the clinician into the Investigator Portal.

Protocol Version 4.0

*Remote enrollment*

In order to better align with clinical practices, Clinical Centers are permitted to conduct consent and enrollment procedures remotely. For potential participants who meet eligibility criteria, and for whom an in-person or remote (i.e., telemedicine) clinical visit occurred, the clinician will facilitate a handoff to the study team who will reach out to initiate the consent process. Having the option to provide informed consent remotely minimizes risks to potential participants who have telemedicine visits and would be coming to the clinic solely to consent (i.e., patients who come to medical centers for in-person appointments often use public transport, and wait in common waiting areas, increasing their exposure risk to respiratory diseases including the seasonal flu, common cold, and coronaviruses). Please see Appendix 6.2 Remote Enrollment Pathway for additional operational details.

Protocol Version 4.0

2.2. Data Collection

The schedule for data collection schedule is outlined in Table 3. There are no planned in-person study visits outside of normal clinical practice, as was done in another large, pragmatic, comparative effectiveness trial in respiratory disease.⁴⁶ Minimal baseline data required for enrollment and randomization will be keyed into the Investigator Portal by Site Coordinators. Follow-up data for the primary outcome (all-cause hospitalization or death) will be collected via the Participant Portal, the RELIANCE Call Center, and ad hoc reporting by Site Coordinators on the Investigator Portal. Medicare administrative/claims data will be collected via a collaboration with the FDA Sentinel Program. Those data along with vital status data from the NDI will be used to assess the completeness of outcome ascertainment.

Data will be collected directly from the patients via the Participant Portal or the Call Center, if the patients are unable or unwilling to access the Participant Portal. All calls completed by Call Center personnel will be recorded for quality assurance and training purposes using HIPAA-compliant telephony software integrated into the Call Center's Voice Over Internet Phone (VOIP) system. The recordings will be retained throughout the project and up to 3 years after final data analysis and publication is complete. The recordings will be stored locally on a HIPAA-compliant University of Illinois Hospital secure server. The server is maintained by UIH Information Systems Management and adheres to all UIH compliance measures. The recordings will be stored in a private folder accessible only to the PI ([name]) and designated project staff who have a specific project-related need to access. Documentation of security measures used by the telephony software management company has been submitted to the IRB for reference. The recording of these calls for operational purposes is noted in the informed consent form participants will review and sign prior to enrolling. Call Center personnel will be able to view a screen with patient contact information housed within the data management system, i.e., call lists that contain patient's names and phone numbers. In general, there is no need to print protected health information (PHI) data at the Call Center. If a printout is required to complete a specific task, those printouts will be stored in a secure location, locked office or locked file, with access limited to study personnel, and will be destroyed once they are no longer needed or within 24 hours, whichever comes first.

Patients will be queried 1 week after randomization to record if they filled the prescription for the study treatment, and if so, the out-of-pocket cost. Patients will be queried at 3 months and 6 months after randomization during the first year of participation, and then every 6 months until a

Protocol Version 4.0

primary outcome (hospitalization or death) is observed.

Site Coordinators will be asked to assist in locating patients who are lost to follow-up and in ascertaining or verifying hospitalizations and death. Site Coordinators will also submit data on patient outcomes, such as adverse events, all-cause hospitalization, changes to study medications, medical diagnoses, or other relevant information, and microbiology cultures in which macrolide-resistant organisms were identified in sputum from the EHR via ad hoc and end-of-study reports on the Investigator Portal ([Table 3](#)). We will ascertain vital status on all patients via the NDI after follow-up is completed.

In addition, we will work with the FDA Sentinel Operations Center (SOC) to obtain Medicare data regarding the claims for study medications and healthcare utilization for patients enrolled in Medicare.

Protocol Version 4.0

Data item	Sources (and estimated time for patients)	Baseline (BL)	1 week	3 and 6 mos after randomization, then every 6 mos until primary outcome is recorded or 36 months after start of enrollment, whichever occurs first.	End of study
Informed consent	Investigator Portal	X			
Demographics	Investigator Portal (3 min)	X			
Smoking status	Investigator Portal	X			
	Participant Portal/Call Center (2 min)			X	
PROMIS questionnaires (physical function, sleep disturbance, fatigue, anxiety, depression)	Investigator Portal	X			
	Participant Portal/Call Center (2 min)		X (if not done at BL)	X	
Height, weight	Investigator Portal	X			
	Participant Portal/Call Center (2 min)			X	
Study treatment (adherence, treatment discontinuation, cross-over to alternate medication)	Investigator Portal	X			
	Participant Portal/Call Center (3 min)		X	X (and ad hoc)	
	Claims databases				X
Out-of-pocket costs	Participant Portal/Call Center (2 min)		X	X	
Healthcare utilization	Investigator Portal	X			X
	Participant Portal/Call Center (5 min)		X	X (and ad hoc)	
	Claims databases				X
	National Death Index				X
Adverse events (hearing decrement, diarrhea, nausea, suicidal ideation)	Participant Portal/Call Center (3 min)		X	X (and ad hoc)	
	Claims databases				X
Adverse event (microbiology cultures of macrolide resistant organisms in sputum)	Investigator Portal				X

Protocol Version 4.0

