3.1. Sample Size

RELIANCE is a randomized, pragmatic, comparative effectiveness trial designed to evaluate whether azithromycin is non-inferior to roflumilast in high-risk patients with COPD for prevention of hospitalizations or death. Our choice of a non-inferiority margin of 1.2 was based upon a recently completed clinical trial in COPD, as well as opinions solicited from clinicians and patients^{48,49}. In a survey of 48 clinicians, the minimum clinically important difference was identified to be 1.2 or higher by 75% of the survey participants and the margin of 1.2 was the most commonly selected (33%). An online survey of 50 patients conducted by the COPD PPRN identified a range of different effect sizes, which seemed to vary based on the history of previous COPD exacerbations, and hospitalizations, and tolerance for adverse effects. A margin of 1.2 is within the range of interest expressed by patients. The planned recruitment period is 30 months with an additional 6 months of follow-up. A sample size of 3,200 provides 92% power with a 1-sided type I error of 0.025 to establish non-inferiority based upon a log-rank test with a margin of HR = 1.2 (azithromycin: roflumilast) assuming: (1) the true HR = 1, (2) the cumulative percent with an event at 1 year is 30%, and (3) a 5% loss to follow-up per year (14.3% cumulatively). Post-hoc analyses of trials suggest that while roflumilast appears to benefit both past and current smokers, the benefits of chronic azithromycin may be limited to past smokers.^{34,50} Accordingly, we will monitor treatment outcomes stratified by current vs. former smoking status and present these results to the DSMB to evaluate the relative safety/efficacy of the two treatments. If the lower bound of the 99% CI for azithromycin exceeds 1.5 at any interim analysis, we will recommend to the SC that the current smoking strata be terminated. The sample size of 3,200 participants provides 89% power to detect a heterogeneous effect based upon smoking status (HR = 1 for roflumilast vs HR = 1.538 for azithromycin for current vs former smokers) assuming a reference cumulative incidence of 30% at one year for current smokers in both treatment groups, equal recruitment to all four subgroups, 5% loss to follow-up per year (14.3% cumulatively) and a two-sided type I error rate. These analyses were computed using PASS software and SWOG Statistical tools, respectively.^{51,52}

Protocol Version 4.0

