There is considerable debate about the optimal approach to analysis of non-inferiority trials, as randomized or per protocol. The major concern about as randomized analyses for non-inferiority hypotheses is that if a significant number of patients do not adhere to their assigned treatment, the test treatments may falsely appear to have similar effects thereby introducing a bias favoring a conclusion of non-inferiority. Per protocol analyses, which limits the analyses to the subgroup of patients who adhere to their assigned treatment, are recommended for testing non-inferiority hypotheses primarily to avoid this potential bias. However, per protocol analyses of non-inferiority trials have all the same flaws as they do in superiority trials.⁵³ For example, if patients discontinue study assigned treatments because of side effects, the potential decreased effectiveness of the treatment is correctly attributed to the assigned treatment in an as randomized analysis but would not be in a per protocol analysis. The preferred approach is to maintain as randomized ITT as the primary analysis and to institute performance measures that ensure the integrity of the trial and provide essential information for interpretation of the results.⁵⁴ Per protocol analysis will be a key secondary analysis and will be compared with the as randomized analysis. Data on protocol performance such as treatment adherence, losses to follow-up and missing data will be used to help understand and interpret differences, if any, in the results of the two methods.

The primary outcome is the time to first all-cause hospitalization or death. Individuals without an event will be censored at the date of last contact. A Cox proportional hazards model will be used to assess whether azithromycin is non-inferior to roflumilast. Non-inferiority will be achieved if the upper boundary of the confidence interval for the hazard ratio (azithromycin/roflumilast) is

Protocol Version 4.0

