3.4. Missing Data

As noted in the IOM Guidelines, prevention is the most important method for handling missing data.⁵⁷ The recommended strategies include careful consideration of potential barriers to data collection during the design phase of the trial, including patient and outcome selection. For example, an advantage to our choice of the primary outcome, all-cause hospitalization or death, is that it can be measured and confirmed from numerous sources. The primary source of outcome data will be from patients. In addition, we have planned a number of strategies to limit missing data during the execution of the trial. As noted above, we will rely on several sources of data to ascertain the primary outcome measures of all-cause hospitalization and mortality including patient reports supplemented by administrative data from CMS and the NDI and follow-up data collected by Site Coordinators. For patient-reported outcomes, we will employ several strategies to prevent missing data, including collection of multiple contacts, verification of phone numbers, email addresses, and secondary contacts including relatives or neighbors, and healthcare providers. Patients will be reminded about outstanding questionnaires via emails and texts backed-up with phone calls. Clinical centers will review the EHR periodically and administrative sources will also be used to identify unreported events. If we are unable to contact the patient via those measures, Site Coordinators will be asked to “find” those patients and collect the missing data. We will also employ real-time data performance reporting so that we can monitor trends in missing data to identify problems and develop interventions. Data on treatment adherence and outcomes will be extracted from CMS administrative database on the subset of patients enrolled in Medicare via a collaboration with the FDA Sentinel Program. We will also use the NDI to identify unreported

Protocol Version 4.0

deaths in the entire study group.

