3.5. Interim Analysis

A single, formal, interim efficacy analysis will be performed once 50% of the information has been collected (i.e., 684 of the expected 1368 event of hospitalization or death have been observed).

The trial will be stopped early only if one of the two treatments is demonstrated to be superior, i.e. it will not stop if the non-inferiority criteria are met. Based upon an O'Brien-Flemming type boundary, the type I error rate would be 0.00305 for the interim analysis and 0.04695 at the final analysis to maintain a global 0.05 error rate over the course of the trial for the superiority comparison.

Protocol Version 4.0

4. Human Subjects

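### Table 3 schedules no participant contact at study close, so hospitalizations in the last 0 to 6 months rest on secondary sources and the stated 92% power is not secured

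*Protocol*

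**What the plan says.** **Contact schedule.** Section 2.2 and the PICOTS Timing row set contacts at 1 week, 3 months and 6 months after each participant's randomization, then 6-monthly. The Table 3 column heading ends the series with "every 6 mos until primary outcome is recorded or 36 months after start of enrollment, whichever occurs first". The first clock is personal and the cap is a calendar date.

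**End of study.** In Table 3, healthcare utilization is marked at End of study for the Investigator Portal, claims databases and the National Death Index (NDI). No Participant Portal/Call Center row is marked in that column.

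**Sources.** Section 3.4 states: "The primary source of outcome data will be from patients". The PICOTS Outcomes row admits trial data and the NDI to the primary analysis and adds Medicare data only for secondary analyses.

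**Censoring.** Section 3.2: "Individuals without an event will be censored at the date of last contact".

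**Planned follow-up and information.** Section 3.1: "The planned recruitment period is 30 months with an additional 6 months of follow-up", and "A sample size of 3,200 provides 92% power with a 1-sided type I error of 0.025". Section 3.5 sets the interim look when "684 of the expected 1368 event of hospitalization or death have been observed".

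**The concern.** The contact schedule and the sample-size calculation imply different follow-up. The calculation credits each participant with 6 to 36 months, up to the calendar close. The schedule stops asking at the last 6-month anniversary before the close. For example, a participant randomized in month 25 has 11 months of potential follow-up, but the last scheduled query is at 6 months.

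Three things are at stake:

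- **Lost events.** Hospitalizations in the gap that do not appear in site records may never reach the primary analysis.
- **Uneven ascertainment of the composite.** The NDI searches for deaths in all participants, whereas admissions in the gap are found only where a site, the EHR or an unprompted report picks them up.
- **Events and time at risk that do not match.** If an event found later by a site or the NDI counts, it sits beside event-free participants who were censored at an earlier last contact and contribute no time at risk in the same window.

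**Working it through.** **Inputs (Protocol 3.1, 3.5 and Table 3).** N = 3200; margin 1.2; true HR 1; one-sided alpha 0.025; 30% with an event at 1 year; 5% loss per year; 30 months of entry plus 6 months; 1368 expected events. Assumptions added here: exponential event and loss times, and uniform accrual.

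**Step 1. Rates.** Event hazard λ = −ln(0.70) = 0.3567 per year. Loss hazard μ = −ln(0.95) = 0.0513. Sum h = 0.4080, so exp(−h) = 0.70 × 0.95 = 0.665, and λ/h = 0.8743.

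**Step 2. Reproduce the stated figure.** Potential follow-up T is uniform on 0.5 to 3 years.

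- Mean of exp(−hT) = (0.665^0.5 − 0.665^3) / (2.5 × 0.4080) = (0.8155 − 0.2941) / 1.0199 = 0.5112.
- Events = 3200 × 0.8743 × (1 − 0.5112) = about 1367.5 (stated: 1368).
- Power = Φ(ln 1.2 × √d / 2 − 1.96). With d = 1368: Φ(3.372 − 1.960) = 92.1% (stated: 92%).

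The Protocol's figures are therefore those of follow-up to the close. The match also suggests that uniform accrual was used: a linear ramp-up of entry gives about 1128 events, far from 1368.

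**Step 3. Cut follow-up at the last scheduled contact.** T becomes 0.5, 1, 1.5, 2 or 2.5 years with equal probability. The gap to the close is uniform on 0 to 6 months, mean 3.0.

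- Mean of exp(−hT) = (0.8155 + 0.6650 + 0.5423 + 0.4422 + 0.3606) / 5 = 0.5651. So 0.5651 × 3200 = about 1808 participants (57%) are event-free and not lost at that contact.
- Events = 3200 × 0.8743 × (1 − 0.5651) = about 1217.
- Gap events = 1368 − 1217 = 151, or 11% of the planned total.
- Power at 1217 events = Φ(3.180 − 1.960) = 88.9%.

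**Step 4. Allow for capture by the other sources.** Events = 1217 + 151 × capture share.

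| Share of gap events captured | Events | Power |
|---|---|---|
| 0% | 1217 | 88.9% |
| 25% | 1255 | 89.8% |
| 50% | 1293 | 90.6% |
| 75% | 1330 | 91.4% |
| 90% | 1353 | 91.8% |
| 100% | 1368 | 92.1% |

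Keeping 90% power needs 1265 events, so capture of (1265 − 1217) / 151 = about 32%. Keeping a power that rounds to 92% needs about 1336 events, so (1336 − 1217) / 151 = about 79%.

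**The case against.** The strongest reply is that the gap is not blind. Section 2.2 has Site Coordinators submit all-cause hospitalizations in ad hoc and end-of-study reports. Table 3 allows ad hoc participant reports. Section 3.4 adds periodic EHR review, and the NDI is searched for everyone. Site reports and the NDI both feed the primary analysis. Section 4.1 lets questionnaires run until the study ends, so nothing bars a closing call, and close-out windows are often left to operating procedures or to a statistical analysis plan, which is not at hand.

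Much of this stands, and it rules out three stronger readings that a reader might infer:

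- **That the last months go unobserved.** They do not. Only the direct query to the participant is missing.
- **That 1368 events and 92% power will not be reached, so that Sections 3.1 and 3.5 should be rewritten to about 1220 events, 89% power and a different interim trigger.** The 88.9% figure assumes that no gap event is found, not even a death, although the NDI covers every participant. The sample-size arithmetic is correct for its assumptions. Building zero capture into the plan would contradict its own end-of-study reporting.
- **That the treatment comparison is biased.** The schedule is the same in both arms and nothing in the document shows differential capture. A shift of the composite toward deaths is plausible in direction but cannot be sized.

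What the reply does not remove is the gap for admissions outside site records. The document does not say that site records show admissions elsewhere. Section 3.4 expects virtually complete ascertainment but counts CMS data toward it, and the PICOTS table keeps those data out of the primary analysis. Section 2.3 adds that the final-year quarterly Medicare files are not regarded as complete and run only through the third quarter of 2022. Nor is the missing contact a detail left open: Table 3 is the Protocol's own schedule, and it omits it.

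**Conclusion.** The point holds in limited form. The Protocol fixes a contact schedule that does not reach the close on which its event count and power depend, and the sources left to cover the difference are weakest for outside hospitalizations. About 151 of the 1368 expected events (11%) fall in the window. Power lies between 88.9%, a floor, and 92.1%. The position within that range cannot be determined, because no capture rate is given. Even the floor is only 3.2 points below the recomputed 92.1%. The unequal handling of events and time at risk within the gap is a second, unquantified consequence of the same schedule.

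The sizes rest on uniform accrual and on exponential event and loss times. The absence of a closing participant contact rests on neither. The change is worth making because it is cheap and protects the primary endpoint, not because the trial is shown to be underpowered.

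**What to change.** In Table 3 and Section 2.2, add a Participant Portal/Call Center close-out contact for every participant still event-free, in a fixed window around the common study-end date. Alternatively, move each participant's final 6-monthly contact into that window. Ask for hospitalizations since the last contact, with dates. Because last contact then falls at or near the close for those reached, this also largely removes the mismatch between counted events and censored time.

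Cost: one questionnaire of about 15 minutes (the length given in Section 2.4) through existing channels, for up to about 57% of participants, or no extra contact if the last one is moved.

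If no close-out contact is added, leave the 684-event trigger as it is. In Section 3.1, give expected events and power as a range (1217 to 1368 events; 88.9% to 92.1%) with the capture assumption stated.
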